Randomization and blinding: Subjects meeting the entry criteria at the screening visit will be randomly allocated 1:1 to an active LMMS or a placebo device. The subjects will then be assigned a treatment number. Participant's names and study numbers will be kept in a password-protected database separate from other study records. Random numbers will be generated by a random number generator by the unblinded device manager who will maintain a database with even numbers being assigned to treatment and odd numbers to placebo. This database will not be shared with the PI or other members of the study team before completion of the study. The project manager will be responsible for storing the Juvent devices and the device manager will be responsible for dispensing them to the study staff as determined by the randomization number.

Monitoring of adherence: Data stored on the Juvent devices will be collected by the study team during the six month visit and twelve month visit via a serial connector. The study team will be able to monitor the date, time and duration of each use. The study coordinator will contact subjects bi-weekly to discuss adherence and to provide support.

Six-month visits: Subjects will return to the study site with their Juvent devices. The study team will collect study data from the device via a serial connector. The study team will also review medical status, supplement compliance and to record any adverse events. Additional calcium carbonate/vitamin D3 will be provided if needed.

Twelve-month visit (study completion): Subjects will return to the study site with their Juvent devices. The study team will collect study data from the device via a serial connector. Subjects will return for DXA of hip and spine, pQCT of the tibia and MRI of tibia and spine, as well as a review of medical status, supplement compliance and any adverse events.

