### Safety Reporting

Reports of any unexpected (headache, dizziness, blurred vision, motion sickness, abdominal pain, nausea, low back pain) and serious (events leading to hospitalization or death) adverse events will be prepared by the PI and sent to the safety officer, IRB, CTRC and NIAMS within 36 hours. Reports summarizing other adverse events will be prepared by the Sstudy coordinator and CTRC informatics and sent to the PI and safety officer bi-annually, as follows:

- Subjects will be asked to contact staff with any symptoms or complaints potentially related to the use of the LMMS device.
- Subjects will keep a written record of these symptoms or complaints in the same diary in which they record instances in which they are unable to use the LMMS device (e.g. vacation, illness).
- Adverse event data that are compiled bi-annually will capture any reported symptoms or complaints potentially related to the use of the LMMS device.

An adverse event form has been developed and will be used by the study staff to record any adverse events that may be related to the LMMS intervention. The clinical coordinator will prepare a summary of adverse events according to subject ID and the study statistician will generate a report of adverse event rates within

each study arm. These data will be provided to the PI and safety officer on a bi-annual basis. However, the PI and safety officer will remain blinded to treatment assignment unless the safety officer determines it is necessary to access this information.

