#### Data and Safety Monitoring Activities

The monitoring plan includes the case report forms (CRF) and source data verification of efficacy and safety parameters, the frequency of monitoring visits, regulatory document review, device accountability and compliance review. Monitoring will be conducted according to the University of Pennsylvania sponsor-investigator standard operating procedures.

A report schedule has been developed to meet the goals of the DSMP in accordance with NIAMS guidelines. The report forms are included below. The frequency of data review for this study differs according to the data type and is summarized in the following table.

Data Safety Monitoring Plan: Report Schedule			
Type of Report:	Prepared By:	Provided To:	Frequency:
Unexpected and Related Serious Adverse Events that Increase Risk	PI	Safety Officer, IRB, CTRC, NIAMS	Within 36 Hours
Adverse Events (combined)	Clinical Coordinator, CTRC Informatics Core	PI, Safety Officer IRB, CTRC	Every 6 months Annually
Patient Recruitment, Targets	Clinical Coordinator, CTRC Informatics Core	PI Safety Officer IRB	Monthly Every 6 months Annually
Subject Adherence with Intervention	Clinical Coordinator	PI Safety Officer	Monthly Every 6 months
Data Quality, Deviation from Protocol	Clinical Coordinator, CTRC Informatics Core	PI Safety Officer IRB	Monthly Every 6 months Annually and as needed
Final Analysis: Safety and Efficacy	Statistician	PI, Safety Officer	100% accrual and follow-up

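### The adverse event form and six-monthly compilation are limited to possibly device-related events, although visits and calls ask about all adverse events, so by-arm rates would probably be incomplete

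*Combined protocol and SAP*

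**What the plan says.** The Safety Reporting section applies a relatedness condition at three steps.

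- Participant report: "Subjects will be asked to contact staff with any symptoms or complaints potentially related to the use of the LMMS device". The diary covers these same symptoms.
- Form: its stated purpose is to "record any adverse events that may be related to the LMMS intervention".
- Compilation: "Adverse event data that are compiled bi-annually will capture any reported symptoms or complaints potentially related to the use of the LMMS device".

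After the form, the same section says the coordinator will summarise adverse events by subject and "the study statistician will generate a report of adverse event rates within" each arm. It does not name the data behind those rates.

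Other sections are wider. Under Study procedures, the six-month visit records any adverse events and the twelve-month visit includes imaging "as well as a review of medical status, supplement compliance and any adverse events". The bi-weekly calls (Adherence to Study Drugs) and the in-person monitoring (Study Intervention; Study Compliance) also cover adverse events with no condition on cause. The schedule of visits lists adverse events from additional screening to study completion.

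There is also a 36-hour route, described in two ways. Safety Reporting begins "Reports of any unexpected (headache, dizziness, blurred vision, motion sickness, abdominal pain, nausea, low back pain) and serious (events leading to hospitalization or death) adverse", with no relatedness condition on such events. The report table under Data and Safety Monitoring Activities labels the 36-hour item "Unexpected and Related Serious Adverse Events that Increase Risk".

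**The concern.** A randomised placebo arm allows relatedness to be inferred from the comparison and not presumed event by event. If events are screened for presumed relatedness before they are counted, the comparison can only show effects that somebody already suspected. The first screen is the participant's own opinion, and the plan gives no rule for the staff's judgement.

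This is a trial of bone strength in postmenopausal women. A fall, or a fracture treated without admission, is an event one would want counted in both arms. Staff who followed Safety Reporting literally would leave it off the form if they saw no link to the platform, even though the coordinator had heard of it at a call or visit.

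A second risk concerns attribution. If women guess which device they have, those who believe theirs is active may be readier to blame it for a symptom, and the recorded share of events could then differ by arm.

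**Working it through.** The plan states no adverse event rate, safety margin or safety power, so there is no figure to reproduce. The check is first a comparison of the text and then an illustration.

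**Text.** Follow a non-serious event that nobody attributes to the device, such as a fall without admission.

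| Step | Section | Covered? |
|---|---|---|
| Self-report and diary | Safety Reporting | No: limited to possibly device-related symptoms |
| Bi-weekly call | Adherence to Study Drugs | Yes |
| Six- and twelve-month visits | Study procedures; Study Intervention; Study Compliance | Yes |
| Adverse event form | Safety Reporting | No |
| Six-monthly compilation | Safety Reporting | No |
| 36-hour report | Safety Reporting | Not among the seven named symptoms, and no hospitalisation or death |
| By-arm rates | Safety Reporting | Source not stated; described directly after the form |

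The event can be heard and written in source documents, but no sentence carries it into the by-arm rates.

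**Illustration (all risks and recording shares are assumed).** The inputs from the plan are 83 women randomised 1:1, so 83/2 = 41.5 per arm, and a two-sided 0.05 test. With p̄ = (p0 + p1)/2,

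power = Φ{ [ |p1 − p0| − 1.96·√(2p̄(1 − p̄)/n) ] / √( [p0(1 − p0) + p1(1 − p1)]/n ) }.

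*Equal share recorded in both arms.* Assumed true risks are 30% (placebo) and 50% (active). For all events: p̄ = 0.40, pooled standard error √(0.48/41.5) = 0.1076, unpooled √(0.46/41.5) = 0.1053, so (0.20 − 0.2108)/0.1053 = −0.10 and Φ = 0.46.

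| Share recorded | Placebo | Active | Difference | Ratio | Power |
|---|---|---|---|---|---|
| 100% | 30% | 50% | 20 points | 1.67 | 46% |
| 75% | 22.5% | 37.5% | 15 points | 1.67 | 32% |
| 50% | 15% | 25% | 10 points | 1.67 | 20% |
| 25% | 7.5% | 12.5% | 5 points | 1.67 | 11% |

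A second assumed pair gives the same direction. With 41 per arm and the arcsine method, 30% versus 10% has power 0.646. Halved to 15% versus 5%, it has 0.345. The ratio is 3 in both cases.

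*Unequal share recorded, no true difference.* Assumed true risk is 40% in both arms.

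| Share recorded, placebo / active | Recorded risks | Difference | False ratio | Chance of a significant active-arm excess (nominal 2.5%) |
|---|---|---|---|---|
| 50% / 50% | 20% / 20% | 0 | 1.00 | 2.5% |
| 50% / 70% | 20% / 28% | 8 points | 1.40 | 13% |
| 40% / 60% | 16% / 24% | 8 points | 1.50 | 15% |
| 30% / 60% | 12% / 24% | 12 points | 2.00 | 29% |

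An equal filter loses events and power but leaves the ratio alone. A false ratio needs a filter that differs by arm.

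**The case against.** The best defence is that the by-arm rates may not be filtered at all. The sentence that produces them has no relatedness condition, none of the limiting sentences uses the word only, the six-monthly item in the report table is labelled simply as combined adverse events, and Data Flow sends all collected data to the study database. The statistician could therefore work from everything recorded at visits. This stands to the extent that omission is the natural reading and is not established. It does not remove the conflict between the sections, and the plan never says which set is used.

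A reader might infer that falls, fractures and musculoskeletal events in general would be lost. The documents do not support that: under Safety Reporting, a hospitalised fracture or low back pain goes to the safety officer within 36 hours whatever its cause. The gap is narrower, namely non-serious events outside the named symptoms. The route is not a full answer, because the report table words it more narrowly and the plan does not say whether these reports feed the by-arm rates.

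A reader might also infer that the comparison is biased or cannot be fair. That too goes beyond the text. The threshold is low, since a possible link is enough. The allocation database is withheld from the investigator and study team, and every device emits a masking tone. As shown above, a filter acting equally does not favour an arm. Guessing of allocation is possible, but no document shows it.

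Finally, the trial is described as minimal risk, the device is designated as non-significant risk, and no safety hypothesis is powered. That limits the weight of the point. It does not justify leaving the collection rule inconsistent.

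**Conclusion.** The point holds as an inconsistency with a likely consequence. Safety Reporting limits self-report, the form and the six-monthly compilation to possibly device-related events, while the visits, calls and monitoring have no such limit. On the natural reading, the by-arm rates would omit non-serious events presumed unrelated. The comparison would then be incomplete, and exposed to attribution bias if allocation is guessed; differential filtering is a risk and is not shown.

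The size cannot be estimated from the documents. In the main illustration, recording 75% to 25% of events equally in both arms lowers power from 46% to between 32% and 11% with the ratio unchanged. Unequal recording can produce a false ratio of 1.4 to 2.0. These figures rest wholly on assumed risks and recording shares. The textual finding does not depend on them.

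Separately, the two descriptions of the 36-hour report differ on whether relatedness is required and must be reconciled.

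**What to change.** 1. Reword Safety Reporting so that the form and the six-monthly compilation take in every adverse event learned of at calls, in diaries or at visits, whatever its presumed cause. Widen the instruction to participants to match.
2. Record relatedness as a separate field, completed by staff blinded to allocation, with a short rule for the judgement.
3. State that the by-arm rates use all recorded events, including those sent by the 36-hour route, with possibly related events shown as a subset.
4. Reconcile the wording of the 36-hour report in Safety Reporting with that in the report table.

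The cost is a change of wording, some extra data entry and possibly a form revision. The form is not shown in the documents, so it may already have a relatedness field. No new visits or calls are needed, because the existing ones already ask about adverse events.

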#### Data and Safety Monitoring Activities

The monitoring plan includes the case report forms (CRF) and source data verification of efficacy and safety parameters, the frequency of monitoring visits, regulatory document review, device accountability and compliance review. Monitoring will be conducted according to the University of Pennsylvania sponsor-investigator standard operating procedures.

A report schedule has been developed to meet the goals of the DSMP in accordance with NIAMS guidelines. The report forms are included below. The frequency of data review for this study differs according to the data type and is summarized in the following table.

Data Safety Monitoring Plan: Report Schedule			
Type of Report:	Prepared By:	Provided To:	Frequency:
Unexpected and Related Serious Adverse Events that Increase Risk	PI	Safety Officer, IRB, CTRC, NIAMS	Within 36 Hours
Adverse Events (combined)	Clinical Coordinator, CTRC Informatics Core	PI, Safety Officer IRB, CTRC	Every 6 months Annually
Patient Recruitment, Targets	Clinical Coordinator, CTRC Informatics Core	PI Safety Officer IRB	Monthly Every 6 months Annually
Subject Adherence with Intervention	Clinical Coordinator	PI Safety Officer	Monthly Every 6 months
Data Quality, Deviation from Protocol	Clinical Coordinator, CTRC Informatics Core	PI Safety Officer IRB	Monthly Every 6 months Annually and as needed
Final Analysis: Safety and Efficacy	Statistician	PI, Safety Officer	100% accrual and follow-up

#### Study Compliance

The Juvent platforms will collect the study data electronically. The study team will be able to monitor the date, time and duration of each use. The study coordinator will contact the subject bi-weekly to discuss adherence and to provide support. Adherence data will be collected by the study team via a serial connector and will be supervised by the study coordinator. Adherence feedback will be provided to study participants in bi-weekly

intervals. Subjects will also be monitored in-person during the six month study visit and twelve month study visit to review adherence, supplementation compliance and to record adverse events.

#### Data Flow

Data will be collected and recorded during each study visit. This will be captured on source documents created for this study. All data collected during the course of the study will be entered into the REDcap database. Data and form checks/data processing will be conducted to assure completion, consistency and accuracy. The data will then be analyzed. Additionally, compliance data downloaded electronically from the Juvent devices will be collected and monitored for agreement with study participant self-reporting.

#### Retention of Study Documentation

Study records will be retained in accordance with institutional policies. Currently, the University of Pennsylvania requires all study records to be retained for a minimum of seven years after a trial ends.

#### Data Management

The computer system that will be utilized for this study will be REDcap. The following functions will be supported: Data tracking, data entry, data editing, updating, reporting and statistical analysis.

REDCap, a data capture and archiving system, provides protocol-focused data management solutions. Developed by Vanderbilt University and implemented by an academic consortium consisting of hundreds of academic research institutions, REDCap application's intuitive design and tailored clinical research workflows enable a research team to capture and manage data entirely within the research team (i.e., no need for a dedicated IT-based data manager). REDCap serves as a more secure and robust alternative to traditional Excel and Access databases.

#### Quality Control Procedures

Case report forms will be reviewed by the study coordinator on an ongoing basis for completeness, accuracy and documentation. Quality control procedures will include graphical displays of the data to identify outliers and case-by-case reviews of data that fall outside of the expected ranges for each variable. Magnetic resonance, DXA and pQCT scans will be analyzed and reviewed for quality within three weeks of the study visit. An image quality monitoring system has been put in place as a means to evaluate the adequacy of the acquired images for analysis. Status of data entry and review will be summarized bi-annually. A summary of this information will be provided in the bi-annual safety reports. Any protocol deviations will be reported to the IRB and a list of protocol deviations will be maintained and included with the bi-annual safety reports and annual IRB reports.

#### Study Completion and Close-out Procedures

Once the study has been closed to enrollment and all follow-up data have been collected, the study will be considered to be in the closeout phase. During this phase, the data will be prepared for final analysis, regulatory and reviewing bodies will be notified, the investigational product inventory will be reconciled, and final reports will be completed.

Closeout activities include, but are not limited to, the following:

- Verification that all study procedures have been completed, data have been entered, and the investigational product has been returned to the responsible party.
- Verification that all data queries have been resolved.
- Assurance that correspondence and study files are accessible for external audits.
- Verification that the Penn IRB has been notified of the study's completion; a copy of the notification and any subsequent correspondence will be filed in the study administrative file.
- Final reports will be completed.

#### Participant Notification

Study participants will be notified that their participation in the study is over at the last visit. The PI or study team member will thank the subject for their participation in the trial. If the participants wish to be informed as

to the study's results, a copy of the publication will be mailed or emailed to them, per the participants' request.

## Policies

### **Confidentiality Procedures**

It is the responsibility of the PI to outline and enforce participant confidentiality and data security guidelines. Study staff should be instructed in their responsibilities regarding data safeguards and cautioned against the release of data to any unauthorized individuals without checking with the NIAMS.

Participant confidentiality safeguards include:

- Electronic files: Data identifying participants that are stored electronically should be maintained in an encrypted form or in a separate file.
- Forms: Forms or pages containing personal identifying information should be separated from other pages of the data forms.
- Data listings: Protected health information (such as name, medical record number, etc.) will not be included in any published data listing.
- Data disposal: Computer listings that contain participant-identifying information will be disposed of in an appropriate manner.
- Access: Participant records will not be accessible to persons outside the site.
- Storage: Study forms and related documents retained both during and after study completion will be stored in a secure location.

Additionally, the following elements are required for computer security:

- Passwords: Passwords provide limitations on general access to computer systems and to the functions that individuals can use.
- User Training: Study staff with access to clinical computer systems will be trained in their use and in related security measures.
- System Testing: Prior to the use of a new computer system, and subsequent to any modifications, the system should be tested to verify that it performs as expected.
- System Backups: Backup copies of electronic data should be made at specified intervals. Backups should be stored in file cabinets or secure areas with limited access.

### **Publication Policy**

The principal investigator will have primary authorship responsibility. The PI must check with NIAMS if there are plans to publish data before the study is over.
